***Footnotes from table above:***

- a Subjects that terminate early should return to the study site for the Week 8 assessments.
- b Limited physical examination: skin (including assessment of Fitzpatrick Skin Type at Screening only), lungs, and heart only.
- c To be collected at Screening, Baseline/Day 0, Week 4/Day 28, and Week 8/Day 56. For subjects <18 years of age, if the Baseline/Day 0 visit occurs within 3 weeks of Screening, the Screening lab results may be utilized.
- d Height will be collected at Baseline and Week 8. Weight will be collected at all study visits. Subject to void prior to weight.
- e IGA will be a 5-point scale ranging from clear (0) to severe (4). **IGA should be completed prior to other physician assessments and by the same Evaluator at each study visit.** Overall Assessment of Erythema (0-3 scale) and Overall Assessment of Scaling (0-3 scale) will be completed.
- f Total BSA affected by seborrheic dermatitis will be determined by the subject's hand method, where the subject's hand (including fingers) surface area is assumed to equal 1% of body surface area.
- g The DLQI will be completed by subjects  $\geq$ 17 years of age. The CDLQI will be completed for subjects 9 to 16 years old, inclusive.
- h WI-NRS will be completed by subjects daily at home starting 7 days prior to the Baseline/Day 0 visit to Day 56 (Week 8) visit. Daily WI-NRS will be completed in the evening prior to IP application (except at Baseline and Week 2 when IP is applied at the clinic).
- i Local tolerability assessments to be recorded prior to IP application for the Investigator assessment of skin irritation (Berger and Bowman skin irritation score) and 10-15 minutes post IP application for the subject's '0- 3' burning/stinging assessment. Note for investigator tolerability assessments: reactions at the site of IP application, which may occur post-Baseline, should be differentiated from the preexisting inflammation associated with the subject's seborrheic dermatitis. At Week 4 and Week 8, subjects will provide a recall assessment of burning/stinging experienced post IP application on the day prior to the clinic visit.
- j An assessment for hypopigmentation and hyperpigmentation will be performed by the Investigator at all clinic visits.

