## 6. GENERAL ISSUES FOR STATISTICAL ANALYSIS

### 6.1. Statistical Definitions and Algorithms

#### 6.1.1. Baseline

Baseline is defined as Study Day 1. In general, the last observation recorded before the first dose of study drug will be used as the baseline for all calculations of change from baseline. For assessments where time was recorded, the last observation recorded before the first application of study drug will be used as the baseline observation for all calculations of change from baseline. If the last non-missing assessment is performed on the same date as the first study treatment administration and time is not available, it is assumed that the assessment took place prior to IP application, per study site training, and the assessment will be considered as baseline, except for adverse events (AEs) and medications starting on the first study treatment dose

administration date which will be considered post baseline.

Average weekly baseline WI-NRS is defined as the average of all non-missing scores reported during the last 7 days prior to treatment if at least 4 of 7 evaluable daily WI-NRS questionnaires are available. Daily baseline WI-NRS is defined as the last non-missing assessment prior to the first study treatment.

For subject tolerability assessments, baseline is derived as the last non-missing measurement taken on the day of first application of study drug.

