### **8.2.3. Other Efficacy Endpoints**

Other efficacy endpoints related to average weekly WI-NRS pruritus score:

- Change and percent change from baseline in average weekly WI-NRS pruritus score at Weeks 2, 4, and 8 will be performed using descriptive summaries (mean, median, inter quartile range) by treatment group and study visit using observed values.
- Change and percent change from baseline in average weekly WI-NRS at Weeks 2, 4, and 8 will be analyzed using an analysis of covariance (ANCOVA) model with terms for treatment, pooled study site, and baseline IGA as covariate. The observed value will be used. Statistical comparisons between the treatment groups will be obtained using contrasts. The LS Means, standard errors, 95% and 99% confidence intervals, and p-values will be presented at each visit. These analyses will be performed on the ITT populations. The p-values are nominal and there is no formal inferential testing on other efficacy endpoints.

Other efficacy endpoints related to daily WI-NRS pruritus score:

- Change and percent change from baseline in daily WI-NRS score will be provided by treatment groups along with plots of daily WI-NRS (mean and SD of observed value and percent change from baseline).
- Similar ANCOVA model will be performed for change and percent change from baseline daily WI-NRS every day in the first week, at Weeks 2, 4 and 8 using observed data.

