### 8.3. Other Efficacy Analysis

Other secondary efficacy analysis will be performed for subjects belonging to ITT population on the observed data.

The other secondary efficacy endpoints include:

- Change and percent change in Scalpdex total score from baseline at Weeks 2, 4, and 8.
- Achievement of an Overall Assessment of Erythema (0-3 scale) score of 0 at Weeks 2, and 4.
- Achievement of an Overall Assessment of Scaling (0-3 scale) score of 0 at Weeks 2, and 4.

- Change and percent change from baseline in DLQI/CDLQI at Weeks 2, 4, and 8.
- Change and percent change from baseline in BSA affected at Weeks 2, 4, and 8.
- Change and percent change from baseline in Overall Assessment of Erythema at Weeks 2, 4, and 8.
- Change and percent change from baseline in Overall Assessment of Scaling at Weeks 2, 4, and 8.
- Achievement of an IGA score of ‘clear’ at Week 4.
- Achievement of an IGA score of ‘clear’ at Week 2.
- Achievement of daily WI-NRS score of 0 or 1 at Weeks 2, 4, 8.
- Change and percent change in WI-NRS from average weekly baseline score.

All the categorical analyses involving achievement of Erythema, Scaling, IGA, WI-NRS are summarized using CMH and proportion difference stratified by pooled site and baseline IGA and presented by study visit.

Continuous endpoints including change and percent change from baseline in average weekly WI-NRS, % BSA, Scalpdex, DLQI/CDLQI, Erythema, Scaling at Week 2, Week 4 and Week 8 will be analyzed using an analysis of covariance (ANCOVA) with the factors of treatment, pooled study site, baseline IGA score, and baseline of the variable under analysis. Similar analysis will be performed for daily WI-NRS every day in the first week and at Week 2, Week 4 and Week 8. Statistical comparisons between the treatment groups will be obtained using contrasts. The LS Means, standard errors, 95% and 99% confidence intervals, and p-values will be presented at each visit. These analyses will be performed on the ITT populations.

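### The daily WI-NRS ANCOVAs rest on one pre-dose score and leave the 7-day baseline mean unused, and SAP 8.2.3 and 8.3 specify different covariates for them

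*SAP*

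**What the plan says.** SAP 6.1.1 (repeated in 6.1.7) defines two WI-NRS baselines.

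- Daily: "Daily baseline WI-NRS is defined as the last non-missing assessment prior to the first study treatment".
- Weekly: "Average weekly baseline WI-NRS is defined as the average of all non-missing scores reported during the last 7 days prior to treatment", subject to a completeness rule, "if at least 4 of 7 evaluable daily WI-NRS questionnaires are available".

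The data for both are collected. The footnotes to the SAP schedule of events say "WI-NRS will be completed by subjects daily at home starting 7 days prior to the Baseline/Day 0 visit".

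The daily analyses appear in two places.

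- SAP 8.2.3 says "Similar ANCOVA model will be performed for change and percent change from baseline daily WI-NRS every day in the first week", and continues to Weeks 2, 4 and 8 on observed data. The model it points back to is an "analysis of covariance (ANCOVA) model with terms for treatment, pooled study site, and baseline IGA as covariate".
- SAP 8.3 says "Similar analysis will be performed for daily WI-NRS every day in the first week and at Week 2, Week 4 and Week 8". The model it points back to has the factors "treatment, pooled study site, baseline IGA score, and baseline of the variable under analysis".

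SAP 8.2.3 declares the p-values for these endpoints nominal, with no formal testing.

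**The concern.** A single 24-hour itch score contains day-to-day fluctuation as well as the subject's usual level. A mean of up to seven scores measures the usual level better, and it can explain variation in later scores that the single score leaves unexplained. The plan derives that mean and then does not use it in the daily models.

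The two SAP sections also disagree on whether any WI-NRS baseline is a covariate in those models. Under 8.2.3 the single score enters only through the subtraction that forms the change. Under 8.3 it also enters as a covariate. The two give different standard errors.

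What is at stake is the width of the reported 95% and 99% confidence intervals for itch on each day of the first week. No other between-arm itch model is planned before Week 2, so any description of early onset would draw on these intervals.

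**Working it through.** **Stated figures.** The plan gives no SD, correlation, effect or power for these models, so there is none to reproduce. Its only design figure concerns IGA success and does not bear on this point. It is consistent: (0.65/0.35)/(0.40/0.60) = 2.79, and 300:150 at two-sided 0.01 gives 99.4% power against a stated minimum of 90%.

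**Assumptions (not in the documents).** Daily scores have unit variance. The between-subject share is s = 0.4 to 0.8, and the remainder is a day-to-day residual with lag-1 correlation φ = 0, 0.3, 0.6 or 0.8. Scores g days apart then correlate r(g) = s + (1 − s)φ^g. All seven pre-dose scores are present. Study day has no Day 0 (SAP 6.1.7), so Day 2 is g = 1 from a pre-dose Day 1 score, which the note to SAP Table 3 allows, and g = 2 from a Day −1 score.

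**Formulas.** The SE of the treatment difference is proportional to the square root of the residual variance.

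- Single score as covariate: 1 − r(g)². Once that score is a covariate, change and raw score give the same treatment estimate.
- Set of covariates with variance matrix V and covariances c with the outcome: 1 − c′V⁻¹c.
- Change with no WI-NRS covariate (8.2.3 as listed): 2(1 − r).

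**No serial correlation (φ = 0, r = s).** The 7-day mean carries all the information, with residual 1 − 7s²/(1 + 6s).

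- s = 0.4: 0.671 against 0.840; SE ratio √(0.671/0.840) = 0.893.
- s = 0.5: 0.5625 against 0.75; ratio 0.866.
- s = 0.8: 0.228 against 0.360; ratio 0.795.

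A simulation at correlation 0.5 (300:150, 4000 trials, true effect −0.25) gave SE 0.0874 with the single-score covariate and 0.0751 with the 7-day mean, a ratio of 0.86. Both were unbiased (mean −0.249).

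**Worked case with serial correlation: φ = 0.6, s = 0.5, g = 1.**

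- Single score: r = 0.5 + 0.5 × 0.6 = 0.80; residual 1 − 0.64 = 0.360.
- 7-day mean: variance 0.711, covariance with the Day 2 score 0.604; residual 1 − 0.604²/0.711 = 0.487. Replacement gives √(0.487/0.360) = 1.16, an SE 16% larger.
- Both: covariance of single score and mean 0.674. Explained variance = (0.64 × 0.711 + 0.365 − 2 × 0.80 × 0.604 × 0.674)/(0.711 − 0.674²) = 0.657; residual 0.343; ratio √(0.343/0.360) = 0.98, an SE about 2% smaller.

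**Full range.** SE relative to the single-score covariate, for s = 0.4 to 0.8:

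| φ | Both, g = 1 (earliest Day 2) | Both, g = 7 (Day 7 from a Day −1 score) | Mean replacing single, g = 1 |
|---|---|---|---|
| 0 | 0.893–0.795 | 0.893–0.795 | 0.893–0.795 |
| 0.3 | 0.949–0.885 | 0.916–0.825 | 0.989–0.923 |
| 0.6 | 0.983–0.955 | 0.949–0.878 | 1.170–1.139 |
| 0.8 | 0.996–0.987 | 0.980–0.943 | 1.374–1.364 |

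Across Days 2 to 7, both covariates therefore cut the SE by 11–20%, 5–18%, 2–12% and 0–6% in the four rows. With no stable between-subject part at all (s = 0, φ = 0.8), the ratio for both is 1.000: no gain and no loss.

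**8.2.3 against 8.3.** The SE ratio of change without a WI-NRS covariate to the single-score ANCOVA is √[2(1 − r)/(1 − r²)] = √[2/(1 + r)]. This is 1.195 at r = 0.4, 1.155 at 0.5 and 1.054 at 0.8. Which section is followed thus moves the SE by 5–20%, about as much as adding the mean can.

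**The case against.** The strongest reply is that this is a choice and not an error. Each outcome is paired with its own baseline, daily with daily and weekly with weekly, in line with the general last-observation rule in SAP 6.1.1. Randomisation keeps the comparison unbiased either way. The p-values are nominal and the tested itch endpoints already use weekly averages. That stands, and it limits the point to an optional gain in precision. It does not settle the mismatch between 8.2.3 and 8.3.

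A second reply is that the last pre-dose day may be the best predictor of the next few days. That also stands, and it rules out a tempting reading: that the 7-day mean should replace the single score. With a one-day gap and φ = 0.6, replacement raises the SE by 14–17% on Day 2, one of the days of most interest. It would also lose subjects with fewer than 4 of 7 scores. Neither objection applies to adding the mean beside the single score, with a rule for incomplete diaries.

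A third reply is that the size is assumption-driven. This is correct. The documents supply no correlation, and under strong serial correlation the gain is close to nil.

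**Conclusion.** The point holds as a modest one about precision and specification. The daily models use one pre-dose score, the derived 7-day mean is unused, and two sections give different covariate sets. Adding the mean cannot raise the large-sample SE. Its benefit on Days 2 to 7 runs from none to about 20%, depending on the assumed between-subject share and serial correlation. The figures concern change only; none is shown for percent change, where the single score remains the denominator.

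A reader might infer that the early itch results are biased, or that the WI-NRS success claims are weakened. The documents support neither. Treatment is randomised, these analyses sit outside the testing strategy, and WI-NRS success uses weekly averages. Nor are the daily models the only evidence on speed of itch relief: WI-NRS success at Week 2 is formally tested. Only the day-by-day picture within Week 1 is particular to them.

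**What to change.** In SAP 8.2.3 and 8.3, state one ANCOVA for change in daily WI-NRS, with these terms: treatment, pooled site, baseline IGA, the last pre-dose daily score, and the 7-day baseline mean. If fewer than 4 of 7 scores exist, use the mean of the available pre-dose scores for this covariate only, under its own name, so that no subject is lost and the 4-of-7 rule elsewhere is untouched. Leave the definition of change as it is. Specify the percent-change model separately.

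SAP V3.0 (22-Sep-2022) postdates unblinding (19-May-2022). The report should therefore say which of the two listed models was run as planned, and show the two-baseline model beside it as supportive and labelled post hoc, as SAP sections 1 and 10.1 require for later additions.

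The cost is one degree of freedom, one derived covariate and two edited paragraphs. No new data are needed, and the testing strategy does not change.

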#### **8.2.4. Overall Assessment of Erythema**

The assessment is performed at Screening, Baseline, and Weeks 2, 4, and 8. The score is reported in ordinal scale with severity grades ranging from 0-3. [Table 4](#) illustrates description of erythema grades.

**Table 3: Erythema Grades**

Score	Description
0	None: No evidence of erythema
1	Mild: Barely perceptible erythema which is faint or patchy
2	Moderate: Distinct erythema,
3	Severe: Intense (fiery red) erythema

Secondary endpoint that is included in the multiple testing scheme is

- Achievement of an Overall Assessment of Erythema (0-3 scale) score of 0 at Week 8

The analysis of Erythema of 0 is performed similar to the primary endpoint including the sensitivity analysis on both imputed and observed data.

Analysis of efficacy endpoints related to erythema score will be performed using ITT population using observed value:

- The number and percentage of subjects in each category will be summarized by treatment and study visit descriptively
- An ANCOVA model similar to what is defined in [Section 8.2.3](#) will be used for analysis of the change and percent change from Erythema baseline.

#### **8.2.5. Overall Assessment of Scaling**

This assessment is performed at Screening, Baseline, and Weeks 2, 4, and 8. The score is

reported in ordinal scale with severity grades ranging from 0-3.

[Table 5](#) illustrates description of scaling grades.

**Table 4: Scaling Grades**

Score	Description
0	None: No scaling evident on lesions
1	Mild: Barely detectable, scattered, small flaking scales
2	Moderate: Scales clearly visible and prominent
3	Severe: Coarse, thick scales, with flaking into clothes or skin

The analysis of Scaling will be performed similar to those of erythema score as indicated in [Section 8.2.3](#).

Separate listings of IGA, average weekly WI-NRS, daily WI-NRS score, Overall assessment of Erythema, and overall assessment of scale score will be provided along with IGA success, and WI-NRS success flag.

Table 6: Summary of Primary and Secondary Efficacy Analyses

Efficacy Endpoint	Primary Analysis	Sensitivity or Supplemental Analysis
Primary		
IGA Success (IGA score of '0' or '1' plus at least 2-point improvement from baseline) at week 8	ITT, multiple imputation (CMH)	#1 PP, observed data (CMH) #2 mITT, multiple imputation (CMH) #3 ITT, observed data (CMH) #4 ITT, non-responder imputation (CMH) #5 ITT, Tipping point #6 ITT based on different site pooling strategy #7 ITT without site stratification
Secondary		

Family 1 ( $\alpha=0.0033$ ): Average weekly WI- NRS Success (achievement of at least a 4-point improvement) at Weeks 2, 4, 8	PRU4-ITT population, multiple imputation (CMH)	#1 PRU4-ITT, observed data (CMH) #2 PRU4-ITT, non-responder imputation (CMH)
Family 2 ( $\alpha=0.0067$ ): IGA Success at weeks 4	ITT, multiple imputation (CMH, odds ratio)	#1 ITT, observed data (CMH) #2 ITT, non-responder imputation (CMH)
Family 2 ( $\alpha=0.0067$ ): Scaling score of '0' at weeks 8	ITT, multiple imputation (CMH, odds ratio)	#1 ITT, observed data (CMH) #2 ITT, non-responder imputation (CMH)
Family 2 ( $\alpha=0.0067$ ): Erythema Score of '0' at Week 8	ITT, multiple imputation (CMH, odds ratio)	#1 ITT, observed data (CMH) #2 ITT, non-responder imputation (CMH)
Family 2 ( $\alpha=0.0067$ ): IGA score of '0' at Week 8	ITT, multiple imputation (CMH)	#1 ITT, observed data (CMH) #2 ITT, non-responder imputation (CMH)
Family 2 ( $\alpha=0.0067$ ): IGA Success at Week 2	ITT, multiple imputation (CMH)	#1 ITT, observed data (CMH) #2 ITT, non-responder imputation (CMH)

### 8.3. Other Efficacy Analysis

Other secondary efficacy analysis will be performed for subjects belonging to ITT population on the observed data.

The other secondary efficacy endpoints include:

- Change and percent change in Scalpdex total score from baseline at Weeks 2, 4, and 8.
- Achievement of an Overall Assessment of Erythema (0-3 scale) score of 0 at Weeks 2, and 4.
- Achievement of an Overall Assessment of Scaling (0-3 scale) score of 0 at Weeks 2, and 4.

- Change and percent change from baseline in DLQI/CDLQI at Weeks 2, 4, and 8.
- Change and percent change from baseline in BSA affected at Weeks 2, 4, and 8.
- Change and percent change from baseline in Overall Assessment of Erythema at Weeks 2, 4, and 8.
- Change and percent change from baseline in Overall Assessment of Scaling at Weeks 2, 4, and 8.
- Achievement of an IGA score of ‘clear’ at Week 4.
- Achievement of an IGA score of ‘clear’ at Week 2.
- Achievement of daily WI-NRS score of 0 or 1 at Weeks 2, 4, 8.
- Change and percent change in WI-NRS from average weekly baseline score.

All the categorical analyses involving achievement of Erythema, Scaling, IGA, WI-NRS are summarized using CMH and proportion difference stratified by pooled site and baseline IGA and presented by study visit.

Continuous endpoints including change and percent change from baseline in average weekly WI-NRS, % BSA, Scalpdex, DLQI/CDLQI, Erythema, Scaling at Week 2, Week 4 and Week 8 will be analyzed using an analysis of covariance (ANCOVA) with the factors of treatment, pooled study site, baseline IGA score, and baseline of the variable under analysis. Similar analysis will be performed for daily WI-NRS every day in the first week and at Week 2, Week 4 and Week 8. Statistical comparisons between the treatment groups will be obtained using contrasts. The LS Means, standard errors, 95% and 99% confidence intervals, and p-values will be presented at each visit. These analyses will be performed on the ITT populations.

Scalpdex questionnaire consists of 23 questions which are categorized into emotions, symptoms and functioning scales. The scale scores and total score are calculated as described in the [Section 6.1.7](#). Analyses of Scalpdex will be limited to subjects in the ITT population who have Seborrheic Dermatitis involvement on the scalp. Change and percent change from baseline for Scalpdex scale scores along with total score are summarized descriptively. In addition, number and percentages for each Scalpdex question is summarized by study visit and treatment group. An ANCOVA model similar to what is defined in [Section 8.2.2](#) will be used for analysis of the change and percent change from Scalpdex (total score, emotions, symptoms and functioning scales) baseline.

Change and percent change from baseline for Overall Assessment of Erythema, Scaling, DLQI, CDLQI, and BSA will be summarized descriptively.

#### **8.4. Subgroup Analyses of Efficacy Variables**

For the primary endpoint of IGA success (IGA of ‘Clear’ or ‘Almost Clear’ plus at least 2-point improvement at Week 8) and tested secondary endpoints, subgroup analysis will be performed using the primary estimand on the following:

- Topical Corticosteroids – Inadequate Response, intolerance or contraindication (Y/N)
- Topical Antifungals – Inadequate Response, intolerance or contraindication (Y/N)
- By age categories (9-17, 18-64 and  $\geq$  65 years)
- By IGA at baseline
- Gender (male, female)
- Ethnicity (Hispanic or Latino, Not Hispanic or Latino)
- Race (White, Black, Others)
- Baseline BSA% (< 5% vs.  $\geq$  5%)
- Baseline BSA% based on tertiles
- Fitzpatrick score of I-III vs IV-VI
- Subjects with facial involvement only vs. subjects with scalp involvement only vs. subjects with facial and scalp involvement

The above subgroup analyses are generated for imputed data only. If odds ratio is not estimable due to zero counts, associated C.I. will not be provided as well. Specifically, if a result is non-estimable, then the CMH test will not include the strata for study site and will not include the strata for baseline disease severity. A footnote in the summary table will indicate this change. For subgroup analysis, no p-value will be provided. Forest plots of subgroup analysis for primary efficacy endpoint and secondary endpoints will be provided.

### **9. SAFETY AND TOLERABILITY ANALYSIS**

All safety analyses will be performed on the Safety population. No inferential statistical tests will be performed.

#### **9.1. Adverse Events**

All the AEs will be coded using the MedDRA dictionary version 24.1.

An overall summary of TEAEs will be provided; this will present number and percent of subjects who reported at least 1: TEAE (including all TEAEs, TEAEs by maximum severity, and TEAEs by greatest relationship), treatment emergent serious adverse events (TESAEs), TEAE leading to discontinuation of the study drug, TEAE leading to study discontinuation, and TEAE resulting in death.

Tables including the number and percentage of subjects will be provided for the following categories:

1. TEAEs by SOC and PT
2. TEAEs by SOC, PT and Maximum Severity
3. TEAEs by SOC, PT, and Strongest Relationship to Study Drug (i.e., related vs. unrelated)
4. TEAEs by PT in descending order
5. TESAE by SOC and PT
6. TEAE leading to discontinuation of the study drug by SOC and PT
7. TEAE leading to study discontinuation by SOC and PT

In the summaries showing severity and relationship to study medication the event with the maximum severity (mild < moderate < severe) or strongest relationship (not related < related) will be reported. If a particular event is missing the severity and/or relationship, then the strongest possible severity or relationship will be assumed for analysis (severity = severe, relationship = likely).

In the AE data listings, all AEs will be displayed. AEs that are treatment emergent will be flagged and AE occurred in the application site will be flagged.

Most frequent TEAE ( $\geq 1\%$ ) of PT will be plotted by treatment groups along with overall incidence of TEAEs and overall incidence of TESAEs.

